Study Objectives	Evaluate the capacity of AMT cream using live bacteria to decrease S. aureus colonization in patients with atopic dermatitis (AD).
Study Design	This is a single center phase 1, double-blind placebo controlled trial
Primary Endpoint(s)	The change in S. aureus abundance after 7 days of AMT cream using live bacteria by using skin swabs to determine the quantity of S. aureus by culture and qPCR.
Secondary Endpoint(s)	
Secondary Lesional AD skin:
 
 1. The abundance of the AMT bacterial strains on lesional skin at baseline and after 1 week BID application of AMT. 2. The quantity of AMT bacterial strains on lesional skin after stopping AMT cream 1 day, 2 days, and 4 days after last application. 3. The change in abundance of Staph aureus on lesional skin from baseline to 1 day, 2 days, and 4 days after stopping AMT. 4. Change in clinical assessments, including SCORAD, modified EASI, and EASI after 1 week BID application of AMT. 5. Identify the diversity of the lesional skin microbiome by DNA sequencing from baseline and after 1 week BID application of AMT. 6. Evaluate the lesional skin microbiome transcriptome by RNA-sequencing analysis from baseline and after 1 week BID application of AMT. 
Secondary Non-lesional skin:
 
 1. The abundance of Staph aureus at baseline and after 1 week BID application of AMT on non-lesional skin. 2. The abundance of AMT bacterial strains on non-lesional skin at baseline and after 1 week BID application of AMT. 3. The quantity of AMT bacterial strains on non-lesional skin after stopping AMT cream 1 day, 2 days, and 4 days after last application. 4. The change in abundance of Staph aureus on non-lesional skin from baseline to 1 day, 2 days, and 4 days after stopping AMT. 5. Identify the diversity of the non-lesional skin microbiome by DNA sequencing from baseline and after 1 week BID application

	of AMT. 6. Evaluate the non-lesional skin microbiome transcriptome by RNA-sequencing analysis from baseline and after 1 week BID application of AMT. 1.
Accrual Objective	27 subjects
Study Duration	2 years
Treatment Description	Autologous microbiome transplant containing commensal Staph species to normalize dysbiosis of atopic dermatitis.
Inclusion Criteria	1. Male or female subjects who are not pregnant or lactating 2. 18-60 years of age 3. Diagnosis of atopic dermatitis for at least 6 months using the Hanifin and Rajka Diagnostic Criteria for atopic dermatitis 4. Presence of lesional atopic dermatitis skin in both antecubital fossae 5. Positive S. aureus colonization based on results of a skin culture taken from one of their AD- affected antecubital fossae during the screening visit 6. Positive for antimicrobial CoNS species from non-lesional AD skin
Exclusion Criteria	1. Use of any topical AD treatments (including topical steroids, topical calcineurin inhibitors) to either arm within one week of the Treatment visit 2. Use of any antihistamines 7 days within one week of the Treatment visit 3. Use of any oral/systemic AD therapies (steroids) within 28 days of the Treatment visit 4. Severe AD that would worsen significantly from holding a participant's usual topical/oral AD medications for the time periods required in the inclusion/exclusion criteria (one week prior to the Treatment visit for topical medications and antihistamines and 28 days prior to Treatment visits for oral medications) 5. Subjects who have taken a bleach bath within a week prior to the Treatment visit, or who take bleach baths during the study 6. Patients with severe medical condition(s) that in the view of the investigator prohibits participation in the study 7. Subjects with Netherton's syndrome or other genodermatoses that result in a defective epidermal barrier 8. Any subject who is immunocompromised (e.g. provides

1.1. Background and Scientific Rationale

It is essential for microbial communities to reside on our epithelial surfaces to maintain several functions of human health (1-3). This conclusion is based in part on observations that dysbiosis, a state of microbial imbalance, is associated with various diseases (1). Systemic antibiotics, bleach baths, or other antimicrobial interventions have been used in patients with Atopic Dermatitis (AD) to attempt to correct dysbiosis (4).

Unfortunately, in addition to promoting the development of antibiotic resistance in pathogens, the nonspecific use of antimicrobials also further disrupts the microbial ecosystem by killing both beneficial bacteria and pathogens. Therefore, the non-specific use of antimicrobials should be avoided when possible.

In this proposal, we describe a novel approach to attempt to treat dysbiosis of the skin surface. We have discovered that many of the strains of coagulase negative *Staphylococcus* (CoNS) that colonize healthy skin, such as *Staphylococcus epidermidis* (*S. epidermidis*), *Staphylococcus hominis*, *Staphylococcus warneri* and *Staphylococcus capitis*, produce antimicrobial activity against *Staphylococcus aureus* (SA). This activity is selective and kills many pathogens but does not inhibit the growth of the normal resident species. AD subjects have a deficiency in the abundance of bacteria that produce this activity. We hypothesize that reapplying the host's own antimicrobial bacteria will facilitate elimination of SA colonization.

We propose here to exploit the antimicrobial function of the microbiome as therapy of skin disease. We will apply skin commensal microbes that have been pre-identified to have antibacterial (anti-*S. aureus*) activity. These beneficial bacteria will be selected from the subject's own resident skin flora (autologous) and expanded in vitro for reapplication. We wish to determine if this approach will eliminate or reduce *S. aureus*, and how long this will last. Thus, the immediate significance of our work will be to show how the microbiome can be used to inhibit SA colonization on the skin. However, the long-term significance of this work will be that it will set the groundwork to test if such a transplant of skin commensal bacteria can be of lasting clinical benefit to patients with AD. This work will therefore also examine key variables to enable later tests of the capacity to alter the microbiome over a longer time period. If successful, the current project will permit future test of functions of the skin microbiome such as immune regulation and barrier development (5-9).

1.2. Rationale for Selection of Investigational Product or Intervention

Unlike healthy control skin, the skin of patients with atopic dermatitis (AD) is frequently colonized by *Staphylococcus aureus* (*S. aureus*) (Leyden JJ et al. 1974), putting these patients at increased risk of *S. aureus* skin infections. In addition, research in our lab has shown that these patients have fewer protective *Staphylococcal* species such as *Staphylococcal epidermidis* (*S. epidermidis*) that are known to produce antimicrobial peptides that play a role in protecting the skin from invading pathogens. In this study, we will attempt to decrease *S. aureus* colonization and increase colonization by protective Staph species in AD patients by first culturing the bacteria on subjects' lesional AD skin. We will selectively grow the subject's *S. epidermidis* colonies and place them into Cetaphil moisturizer. This will be a single site, double-blind, randomized phase 1 clinical trial evaluating a novel therapy for atopic dermatitis, an autologous microbiome transplant (AMT).

[figure not shown]
1.3. Preclinical Experience

This proposal introduces the innovative concept of autologous microbial transplant (AMT) therapy. The principle of skin AMT therapy is to isolate a subset of the subject's own microbes with beneficial functions, expand them in vitro, and then to transplant these specific microbes back onto diseased sites of the same subject. We have developed a novel high-throughput screening technique to select these microbes from skin flora. This therapy can be an attractive alternative to antimicrobial therapy because we use bacteria already on the subject and these microbes have therefore already demonstrated the capacity to be tolerated by the subject and not to cause disease. This theoretically reduces the risk compared to non-native species/strains. Thus, we believe the concept of AMT is attractive and innovative.

[figure not shown]
Our group's prior research has focused on the underlying molecular mechanisms for the microbial symbiosis that benefits our cutaneous immune system and homeostasis. In a 2009 publication in *Nature Medicine*, our group first demonstrated an anti-inflammatory benefit of *S. epidermidis*, a predominant CoNS species on normal human skin(6). We have also demonstrated that a small molecule of <10 kDa secreted from *S. epidermidis* increased expression of β -defensins in murine skin and human keratinocytes, enhancing resistance to pathogens of mice at a steady state (5). Other groups also have shown that a product secreted from *S. epidermidis* strongly sensitizes the host's innate immune system to pathogens (7). In cultured human keratinocytes, activation of TLR2 by peptidoglycan, the major constituent of gram-positive cell walls, strengthens cellular tight junctions (9). More recently, it was demonstrated that skin commensal bacteria enhanced cutaneous T-cell functions via activation of IL-1 signaling (8). Indeed, mono-colonization of germ-free mouse skin by *S. epidermidis* protected these mice against pathogen infection (8).

Some strains of *S. epidermidis*, often the dominant bacteria found in the skin microflora, produce various types of antimicrobials (10). Because of their potential to kill pathogens in vitro, these antimicrobials can provide antimicrobial protection against pathogens on the skin surface. We have published several examples of this (5, 11), and are characterizing more by using our innovative screening technique. These findings indicate that multiple CoNS species inhabiting the surface of normal human skin can be a source of antimicrobial activity and contribute directly to the skin's antimicrobial defenses. Also, this shows an additional benefit that may be derived from this study. By isolating diverse clones of antimicrobial bacteria we may discover several new antimicrobials

Figure 1 shows the high-throughput technique for screening CoNS strains that produce antimicrobial activity against SA. This technique enables us to determine the frequency of antimicrobial CoNS strains on the skin and then select them for transplant. Preliminary data shown in our introduction to the revised protocol has illustrated how AD patients colonized by SA have a lower frequency of antimicrobial CoNS species than normal healthy skin or *S. aureus*-negative AD patients. The profile of these antimicrobial CoNS was determined to be different from that of non-antimicrobial species by sequencing of the full-length 16S rRNA gene of each clone. These findings show that the human skin harbors diverse Staphylococcal strains providing antimicrobial activity, and that a low frequency of antimicrobial CoNS may partially account for the susceptibility of AD skin to infection by SA. All subjects studied to date harbor CoNS species that will inhibit SA. Thus, a source of microbes for AMT is available on most subjects even though AD subjects have fewer available with this activity than normal subjects.

Preliminary work has identified an excellent vehicle for AMT. Clinical isolates of antimicrobial strains of *S. hominis* or known antimicrobial strains of *S. epidermidis* (ATCC12228) (12) were mixed with several different over-the-counter skin moisturizer creams at 1×10^7 CFU/gm. Cetaphil® Moisturizing Lotion (Galderma, TX) was found to be an excellent bacteriostatic vehicle. This formulation retained the viability of antimicrobial *Staphylococcus* for over 5 days at room temperature, but did not allow bacteria to grow (100% at day-2 and 50% at day-5). This formulation was active. A single topical application of this cream formulation containing a known antimicrobial strain of *S. epidermidis* (ATCC12228), or newly discovered antimicrobial strain of *S. hominis*, were found to successfully decrease *S. aureus* colonization on the skin of mice within 29 hrs in comparison to vehicle or similar formulations of known non-antimicrobial *S. epidermidis* strain (ATCC1457) (Fig.2). These data show that AMT on humans is likely to inhibit *S. aureus* colonization.

Clinical Studies

N/A

1.4 Clinical Studies

In order to further examine if topical application of antimicrobial CoNS can decrease *S. aureus* survival on the skin of AD subjects, we conducted a preliminary double-blind, placebo-controlled autologous microbiome transplant study (AMT) under IND# 15786. An antimicrobial CoNS strain was isolated from the non-lesional

skin of each of 5 AD subjects who were *S. aureus* culture positive. To transiently increase their abundance on each subject, the active strains were expanded and then reapplied to the lesional forearm skin of the same subject, from which the active colonies were isolated, to a final concentration of 1×10^5 CFU/cm², a density similar to previous assessments of the abundance of bacteria on normal human skin. A single application of this functionally defined and autologously-derived CoNS strain(s) decreased *S. aureus* CFU within 24 hours; whereas, vehicle applied to the contralateral arm in a double-blind comparison did not (Fig. 4a-b). However, CoNS survival on the arm 24 hours after AMT was similar to the baseline. These results suggest that a single application of CoNS at a dose of 1×10^5 CFU/cm² was sufficient to transiently decrease survival of *S. aureus*, but the majority of transplanted CoNS died within 24 hours. Therefore, we propose to apply the AMT cream for multiple applications (BID for seven days) for better survival of transplanted CoNS.

[figure not shown]

Figure 4. Transplantation of antimicrobial CoNS reduces survival of *S. aureus* colonized on the skin surface.

Figure 4 panel (a) demonstrates the effect of transplantation of antimicrobial CoNS strain(s) on survival of *S. aureus* on the skin surface of subjects with AD. *S. aureus* survival was measured on the lesional sites in both antecubital fossa of the AD subject before and 24 hours after either treatment with antimicrobial CoNS strain(s) autologously screened from the same subject or vehicle. Panel (b) illustrates *S. aureus* survival on the forearm 24 hours after treatment with autologous strain(s) of CoNS or treatment with vehicle. Relative CFU of *S. aureus* is shown as percent of baseline and different color symbols indicates data from each individual subject. In panel (c) CFUs of CoNS on the skin surface of subjects with AD were simultaneously counted as shown in panel (a). Panel (d) shows CoNS survival on the forearm 24 hours after treatment with autologous strain(s) of CoNS or treatment with vehicle. Relative CFU of CoNS is shown as percent of baseline.

In our pilot study of 5 subjects evaluating an AMT cream (IND#15786), we noted no serious adverse events (SAEs). Two subjects noted mild worsening of AD, which were deemed unrelated to the AMT cream given AMT cream was not applied on the area with worsening AD. One subject noted mild worsening of AD with an increase in pruritus and erythema on both arms. Since AMT was applied to only one arm, it is less likely that

the adverse event (AE) was related to the AMT cream given the bilateral worsening of AD on the upper extremities. Overall, the AMT cream was very well tolerated and had no significant adverse events.

2. Study Hypotheses/Objectives

Our preliminary data strongly suggest that some strains of resident CoNS act to defend the skin surface against colonization by SA. The goal of this proposal is to restore this function of the microbiome on atopic skin by replacing these beneficial bacteria. Our approach will be very safe since we will select the beneficial microbes that are normal residents of healthy skin. These bacteria will be harvested from the subject, expanded and reapplied to the same subject. An FDA IND has been approved and institutional IRB obtained for this approach (IND #15786). After application of the bacteria the survival of SA will be measured. Thus, this autologous microbiome transplant (AMT) is a first step before a generalized “probiotic” therapeutic approach.

We propose here a randomized, double-blind, placebo-controlled trial that will apply beneficial bacteria from the AD host onto lesional skin of AD patients, thus performing an autologous microbiome transplant. The transplanted bacteria have been selected based on their capacity to inhibit *S. aureus* colonization. Our central hypothesis is that this intervention will decrease colonization of *S. aureus* and normalize immune functions of AD skin. This hypothesis will allow us to evaluate the function of the microbiome in AD, and normalize host defense properties in AD, and to develop an intervention that is highly likely to decrease *S. aureus* colonization and may also improve skin inflammation. During the course of this trial we will also obtain vital information to further explain how the microbiome functions and what variables control its composition.

Aim Evaluate the capacity of AMT cream to decrease *S. aureus* colonization in patients with atopic dermatitis (AD).

Hypothesis: Transplant of AMT will decrease *S. aureus* on AD skin

Study objectives:

Primary: To determine the change in abundance of *Staph aureus* from baseline after 1 week BID application of AMT.

Secondary Lesional AD skin:

1. To measure the abundance of the AMT bacterial strains on lesional skin after 1 week BID application of transplant.
2. To measure the rate of elimination of the microbiome transplant on lesional skin after stopping application of transplant cream
3. To determine the rate of reappearance of *Staphylococcus aureus* on lesional skin after discontinuing 1 week application of AMT cream.
4. To determine the change in clinical assessments, including SCORAD, modified EASI, and EASI after 1 week BID application of AMT.
5. Evaluate the diversity of lesional skin microbiome by DNA sequencing from baseline and after 1 week BID application of AMT.
6. Measure the difference in microbiome transcriptome on lesional skin by RNA-sequencing analysis from baseline and after 1 week BID application of AMT.

Secondary Non-lesional skin:

1. To determine the change in abundance of *Staph aureus* from baseline after 1 week BID application of AMT on non-lesional skin.

2. To measure the abundance of the AMT bacterial strains on non-lesional skin after 1 week BID application of transplant.
3. To measure the rate of elimination of the microbiome transplant on non-lesional skin after stopping application of AMT
4. To determine the rate of reappearance of *Staphylococcus aureus* on non-lesional skin after discontinuing 1 week application of AMT cream.
5. Evaluate the diversity of lesional skin microbiome by DNA sequencing from baseline and after 1 week BID application of AMT on non-lesional skin.
6. Measure the difference in microbiome transcriptome on non-lesional skin by RNA-sequencing analysis from baseline and after 1 week BID application of AMT.

3. Study Design

3.1. Description of Study Design

This is a single site, double blind placebo controlled study, which will assess the efficacy, safety, and steady state of Autologous Microbiome Transplant (AMT) cream in adults with AD. After providing informed consent, patients will be assessed for study eligibility at the screening visit, in which participants will consent to all of the study experiments separately. Subjects that withdraw from the study will be replaced. Eligible subjects will be randomized to receive either AMT cream or placebo in a 2:1 allocation ratio (AMT cream: placebo).

Subjects will be instructed to apply either the AMT or vehicle cream to both arms twice a day for seven days. Both subjects and clinical investigators will be blinded. Optional follow-up visits to assess clinical effect and steady state may occur at 1 and 4 hours after initial cream application if the subjects are willing to return at these time points. 4 days after the treatment visit, subjects will return to the clinic for fresh aliquots of the AMT and vehicle creams as well as to assess safety and clinical effect. Subjects will return to clinic after the seven day course of AMT or vehicle creams for clinical and safety assessments. Subjects will then be asked to return to the clinic 1 day after completion of the AMT or vehicle cream course for additional safety and clinical effect assessments. Subsequently, subjects will return for additional follow-up visits only if their lesional atopic dermatitis sites have not yet returned to baseline (*S. aureus* is no longer inhibited and *Staph species* from the AMT cream is zero). Up to 27 subjects will be recruited for this entire study. The duration of this study is approximately 2 months. We anticipate the entire study duration will be approximately 2 years total, and that it will take approximately 1 year to reach recruitment and enrollment goals for this study. The study flow diagram is provided in Figure 1.

Intervention(s) and comparators: A coded cream consisting of Cetaphil® Moisturizing Lotion alone, or the microbiome transplant consisting of Cetaphil® Moisturizing Lotion plus 10^{5-8} CFU/gram Cetaphil® of coagulase negative *Staphylococci* clones expressing antimicrobial products isolated from the subject's own non-lesional skin. Since the two creams are indistinguishable in terms of color and texture, both the study coordinator and the subject will remain blinded to the identity of the cream. Our goal is to achieve a density of 1

$X 10^5$ CFU/10mg/cm² at the time of application. This abundance is known to be safe as it is the density of bacteria typically found on normal skin.

[Insert a schematic diagram of the trial here (include study cohorts and sample size, treatment allocation, time points of study intervention and subject follow-ups)]

Table format

Cohort	27 subjects	ARM 1	18 subjects: AMT cream
		ARM 2	9 subjects: Vehicle cream only

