6.2. Study Design – dose schedule

The dosing schedule for the AMT cream or the Vehicle (Cetaphil® lotion) is described in Sections 8.3 and 8.5.

The first dose of the AMT cream or Vehicle cream will be administered to the subjects at the clinical site on Day 0 (Treatment Initiation Visit). At that time, they will be guided and given a handout instructing them to apply the AMT or Vehicle cream uniformly across both arms (this area will include *S. aureus* colonized lesions as well as non-lesional skin) twice daily for seven days. The participants will also be provided a subject diary and 18 single-use containers for dosing at home. An additional 14 single-use packets of AMT Product or Vehicle Product will be dispensed at the next clinic visit on Day 4 to use until Day 7. Subjects will be instructed that 2 additional single-use containers will be provided to them at Day 0 and Day 4 in the event that the subject should misplace a container of study cream. Accountability of the study creams will be performed, and subjects will be asked to return the jars of used and unused cream at the next in-clinic visit.

At the clinic visits on Day 4 and Day 7, the subjects will provide skin swab samples and be assessed for adverse events (AEs). Three additional clinic visits will be scheduled to assess safety and stability of the AMT cream. There will be a 30 day follow-up of all participants after the last treatment to assess safety and disease status. This will be brief phone call, and subjects will be asked to report any new adverse events and to answer questions regarding the status of their AD. Any subject with an ongoing AE/SAE at the time of this phone contact will continue to be followed until the event is resolved with or without sequelae.

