Visit 7 (Day 9 +/- 7): Subjects will be asked to return to the clinic for Visit 7 for follow-up. Subjects will be asked to refrain from bathing, exercising, or showering starting at 12:01am of Visit 7. Vital signs will be taken. Any adverse events since the last visit will be recorded. A brief exam of the skin on subjects' arms will be performed. For subjects with AD, the severity of AD on each arm will be graded using the localized SCORAD, modified EASI, and global SCORAD and EASI grading. Subjects will also be asked to grade their pruritus on a scale of 1-10, with 10 being the worst pruritus of their life. Digital photographs of the lesional skin on both arms will be taken. Next, one culture swab and one to two DNA swabs will be taken from the eczematous skin from each arm, and one culture swab and one to two DNA swabs will be taken from the non-lesional skin on the upper inner arm for a total of up to twelve (12) swabs. We expect this visit to take approximately 15 minutes.

Visit 8 (Day 11 +/- 7): Subjects will be asked to return to the clinic for Visit 8 for follow-up. Subjects will be asked to refrain from bathing, exercising, or showering starting at 12:01am of Visit 8. Vital signs will be taken. Any adverse events since the last visit will be recorded. A brief exam of the skin on subjects' arms will be performed. For subjects with AD, the severity of AD on each arm will be graded using the modified EASI, and global SCORAD and EASI grading. Subjects will also be asked to grade their pruritus on a scale of 1-10, with 10 being the worst pruritus of their life. Digital photographs of the lesional skin on both arms will be taken. Next, one culture swab and one to two DNA swabs will be taken from the eczematous skin from each arm, and one culture swab and one to two DNA swabs will be taken from the non-lesional skin on the upper inner arm for a total of up to twelve (12) swabs. At the conclusion of this visit, subjects may resume prohibited medications, as needed, and may use their choice of soap and emollient. We expect this visit to take approximately 15 minutes.

Visit 9, Phone 2 (Day 38 +/- 7 days)

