13.4.4 Analyses of Secondary and Other Endpoint(s)/Outcome(s)

Secondary Endpoints, Lesional AD skin:

1. The abundance of the AMT bacterial strains on lesional skin at baseline and after 1 week BID application of AMT.
 - a. The abundance of live *CoNS* species on lesional skin will be compared from baseline (day 28) to Day 35 after 1 week BID application of AMT cream versus placebo. This will be calculated using a two-tailed t-test for independent samples with type II error rate of 0.2 and type I error rate of 0.05.
2. The quantity of transplanted bacteria on lesional skin after stopping AMT cream 1 day, 2 days, and 4 days after last application.
 - a. Live antimicrobial *Staph* species will be measured on lesional skin at baseline (day 28), Day 35 (after 7 days of cream application), Day 36, Day 37, and Day 39 in order to evaluate the abundance of the antimicrobial *CoNS* species that remains after

stopping cream application. In order to take into account the variance of the abundance of antimicrobial *CoNS* species found on each subject's skin at baseline, we will perform CFU counts at each time point (Day 28, 35, 36, 37, and 38) and evaluate the percentage of antimicrobial species present at each time point. The percentage of antimicrobial species present at each time point will be compared between the AMT cream arm and placebo arm using a two-tailed t-test for independent samples with type II error rate of 0.2 and type I error rate of 0.05.

3. The change in abundance of *Staph aureus* on lesional skin from baseline to 1 day, 2 days, and 4 days after stopping AMT.
 - a. The abundance of live *Staph aureus* on lesional skin will be evaluated using CFU counting at baseline, 1 hour, and 4 hours after initial application of AMT or placebo cream, and after 4 and 7 days of cream application. At each time point, we will compare the AMT cream and placebo arms by using a two-tailed t-test for independent samples with a type I error rate of 0.05 and type II error rate of 0.2.
4. Change in clinical assessments, including SCORAD, modified EASI, and EASI after 1 week BID application of AMT.
 - a. A modified EASI, global SCORAD and EASI score will be assessed at baseline 1 week BID application of AMT cream or vehicle cream. Using percentage of improvement of these scores, we will compare percent reduction of AD severity between AMT cream and placebo cream using a two-tailed t-test with type I error rate of 0.05.

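### Section 3.1 makes the Day 9 and Day 11 visits depend on the outcome, while Sections 6.2 and 8.3 and Table 1 schedule them for everyone

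*Combined protocol and SAP*

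**What the plan says.** Section 3.1 describes a visit one day after the last application (Day 8). After that, "subjects will return for additional follow-up visits only if their lesional atopic dermatitis sites have not yet returned to baseline". It defines the return to baseline in two parts, both required: "S. aureus* is no longer inhibited and *Staph species* from the AMT cream is zero". No numerical cut-off is given for inhibition.

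Other sections carry no such condition. Section 6.2 states: "Three additional clinic visits will be scheduled to assess safety and stability of the AMT cream". Section 8.3 says of Day 9, "Subjects will be asked to return to the clinic for Visit 7 for follow-up", and of Day 11, "Subjects will be asked to return to the clinic for Visit 8 for follow-up". Table 1 has columns for both visits. Its footnotes mark the repeat culture visit, the repeat phone call and the optional visits as conditional, but not Visits 7 or 8.

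Both days are used in the analysis. Section 13.4.4 numbers baseline as day 28, so its days 35, 36, 37 and 39 are study Days 7, 8, 9 and 11. (The same item also lists day 38 where 39 is expected.) For the transplanted bacteria it states: "The percentage of antimicrobial species present at each time point will be compared between the AMT cream arm and placebo arm". This is written for lesional and for non-lesional skin. The *S. aureus* endpoint also names one, two and four days after treatment ends. Its analysis text, however, covers only baseline, 1 hour, 4 hours, Day 4 and Day 7.

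**The concern.** A site cannot follow both instructions. If it follows Section 3.1, whether a subject is seen on Days 9 and 11 depends on Day 8 *S. aureus* and AMT strain results, which are the quantities the secondary endpoints follow over time.

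The rule would probably act differently in the two arms. The control arm is "9 subjects: Vehicle cream only", so it adds no AMT bacteria. In the pilot, AMT lowered *S. aureus* within 24 hours, whereas "vehicle applied to the contralateral arm in a double-blind comparison did not". Vehicle subjects would therefore tend to be released, and AMT subjects with persisting strains or inhibition would tend to be kept. AMT subjects already back at baseline on Day 8 would be absent from the later part of the elimination curve.

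The rule looks only at lesional sites, so non-lesional data would be lost because of a lesional result. Section 13.4.1 admits anyone with one follow-up visit to the intention-to-treat analysis and has no rule for values missing by design. Recall or release would also pass on information about a culture result that is related to allocation, and no section says who applies the rule.

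**Working it through.** **1. Who would be recalled under Section 3.1.** Release needs both parts of the definition, so a subject is recalled if *S. aureus* is still inhibited or if AMT strains are still found. An AMT subject whose *S. aureus* has rebounded but who still carries strains is recalled. An AMT subject who meets both parts is not. A vehicle subject scored zero for AMT strains is recalled only if *S. aureus* counts as inhibited.

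**2. Controls kept (assumptions; the documents give no figure).** Let the change in log10 *S. aureus* on vehicle by Day 8 be normal with mean m and SD s, and let a fall of at least t count as inhibition. Assume vehicle subjects score zero for AMT strains. The share kept is Φ((−t − m)/s), and the number kept is 9 times that share.

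| Fall needed (log10) | m = 0, s = 0.4 to 1.0 | Of 9 controls | m = −0.3, s = 0.4 to 1.0 |
|---|---|---|---|
| any | 50% | 4.5 | 62–77% |
| 0.5 | 11–31% | 1.0–2.8 | 31–42% |
| 1.0 | 1–16% | 0.1–1.4 | 4–24% |

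For example, with t = 0.5, m = 0 and s = 1.0, Φ(−0.5) = 0.309 and 9 × 0.309 = 2.8.

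**3. The plan's own sample size, used as a yardstick.** Section 13.7 gives means of 192.86 and 19.186 and deviations of 191.86 and 21.42.
- Pooled SD = √((191.86² + 21.42²)/2) = 136.51.
- d = 173.674/136.51 = 1.272.
- A two-sided t-test at 0.05 with 16 + 8 subjects has power 0.802, so the stated n = 24 is reproduced.

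No effect size is given for Days 9 and 11, so this d is borrowed from the *S. aureus* calculation. With noncentrality d√(n₁n₂/(n₁ + n₂)) and all 18 AMT subjects present, power is 0.85 with 9 controls, 0.67 with 5, 0.59 with 4, 0.49 with 3 and 0.37 with 2.

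**4. Selection.** Consider a Day 9 *S. aureus* contrast with no true difference between arms. Assume an SD of 0.7 log10 and a Day 8 to Day 9 correlation ρ of 0.3 to 0.8. All AMT subjects are recalled because strains persist, and vehicle subjects only if *S. aureus* fell by more than t. The expected bias against AMT is ρ × 0.7 × φ(t/0.7)/Φ(−t/0.7).
- Any fall counts: 0.7 × 0.798 = 0.559, giving 0.17 to 0.45 log10. Simulation (6,000 trials per setting) gave 0.16 to 0.44, with type I error 0.08 to 0.17.
- Threshold 0.5: 0.7 × 0.309/0.238 = 0.91, giving 0.27 to 0.73. Simulation gave 0.28 to 0.73, with type I error 0.09 to 0.31. Only about two thirds of simulated trials (67–68%) kept the two controls set as the minimum for the t-test.
- The same *S. aureus* rule selecting in both arms (any fall, ρ = 0.5): bias about 0 and type I error 0.04.

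For antimicrobial CoNS the tendency is the other way. Dropping AMT subjects already back at baseline would overstate persistence among those who remain.

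**The case against.** The strongest reply is that the operative text schedules everyone. Section 8.3 describes Visits 7 and 8 in full, Table 1 leaves them without a footnote, and Visit 6 has no step for reviewing cultures or releasing subjects. The medication hold runs to Visit 8 for all. On this reading the Section 3.1 sentence is overview text that was never put into operation. That stands to this extent: the defect is first a contradiction, and harm follows only if Section 3.1 is obeyed.

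Stronger readings are tempting, but the documents do not support them:
- **The rule removes most or all controls by construction.** AMT strains are autologous, and inclusion criterion 6 requires antimicrobial CoNS on every subject's non-lesional skin. The assays in Section 9.1 separate coagulase-positive from coagulase-negative staphylococci or identify species. None is described that separates transplanted from resident strains, so a vehicle subject need not score zero. Nor is about half the controls an upper limit: a mean vehicle fall of 0.3 log10 keeps 62–77% if any fall counts.
- **Everyone whose *S. aureus* has rebounded is missing.** The two-part definition still recalls those who carry strains.
- **The *S. aureus* reappearance test is biased as written.** That test does not include Days 9 or 11.
- **Recall reveals the cream.** It could hint at allocation, but some controls may be recalled too. The rule acts only after Day 8, so the Day 7 primary endpoint has nominally been collected.
- **The rule cannot be operated because plates need 24 hours.** Visit 7 has a window of ±7 days.

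**Conclusion.** The contradiction is certain from the text: Section 3.1 conditions the visits after Day 8 on the outcome, and Sections 6.2 and 8.3 and Table 1 do not. If Section 3.1 were followed, the written Day 9 and Day 11 comparison of antimicrobial CoNS would be made in a sample selected on the outcome, probably differently by arm, with no rule for the missing values.

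The size is not fixed by the documents. Under the stated assumptions between about 0.1 and 4.5 of 9 controls remain, and more if vehicle lowers *S. aureus* or resident strains are counted as AMT strains. On the borrowed effect size, power falls from 0.85 to 0.59 with 4 controls and 0.37 with 2. The direction of bias is not fixed either: CoNS persistence would tend to be overstated, while an *S. aureus* contrast could run against AMT or, with equal selection in both arms, show no bias. The point should be corrected before the trial starts. It does not undermine the primary analysis.

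**What to change.** Reconcile Section 3.1 with Sections 6.2 and 8.3 and Table 1 by deleting the outcome-dependent condition. State that the Day 9 and Day 11 swab assessments are done in all randomised subjects. This changes one sentence, and the visits are already in the schedule.

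At the same time, reconcile the Section 8.3 passages (Treatment Visit and Visit 8) that tie the end of the medication hold to Visit 8, because a subject released under Section 3.1 would have no Visit 8. What the clinical rule should be is for the sponsor and investigator.

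In Section 13.4.4, align the *S. aureus* analysis times with the days its endpoint names, and correct the day 38/39 discrepancy. If any condition on attendance is kept, report Days 9 and 11 descriptively, with a stated rule for values missing by design. These are text changes only.
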